Appendix 1. Abbreviations

This following is a list of abbreviations that may be used in the protocol.

Abbreviation	Term
AE	adverse event
ACR	american college of rheumatology
ACPA	anti-citrullinated protein antibodies
ALT	alanine aminotransferase
ANCOVA	analysis of covariance
AST	aspartate aminotransferase
AUC	area under the curve
ATP	adenosine triphosphate
BA	bioavailability
BID	twice a day
BBS	biospecimen banking system
BP	blood pressure
C _{max}	peak or maximum observed concentration
CK	creatine kinase
CMV	cytomegalovirus
CRF	case report form
CSA	clinical study agreement
CSR	clinical study report
CT	computerised tomography
CTA	clinical trial application
CTCAE	common terminology criteria for adverse events
CYP	cytochrome p
DCT	data collection tool
DILI	drug-induced liver injury
DMARD	disease-modifying antirheumatic drugs
DNA	deoxyribonucleic acid
DU	dispensable unit
EBV	epstein-barr virus
EC	ethics committee
ECG	electrocardiogram
eGFR	estimated glomerular filtration rate
EDP	exposure during pregnancy
EOS	end of study
EU	european union
EudraCT	european clinical trials database
EULAR	european league against rheumatism
FACS	fluorescence-activated cell sorting
FDA	food and drug administration
FIH	first in human

Abbreviation	Term
FSH	follicle-stimulating hormone
FU	follow up
fu	fraction unbound
GCP	good clinical practice
GGT	gamma-glutamyl transferase
GST	glutathione-S-transferase
HAQ-DI	health assessment questionnaire – disability index
HBcAb	hepatitis B core antibody
HBsAg	hepatitis B surface antigen
HBcAb	hepatitis B core antibody
HIV	human immunodeficiency virus
hsCRP	high-sensitivity C-reactive protein
HSV	herpes simplex virus
IC50	50% inhibitive concentration
ICH	international conference on harmonisation
ID	identification
IgA, G, M, E	immunoglobulin of the A, G, M , E isotypes
IGRA	interferon-gamma release assay
IL	interleukin
IND	investigational new drug application
IFN	interferons
INR	international normalized ratio
IP	investigational product
IRB	institutional review board
IRC	internal review committee
IRT	interactive response technology
ITT	intent to treat
IUD	intrauterine device
IV	intravenous
IWR	interactive web response
JAK	janus kinase
K ₂ EDTA	dipotassium ethylenediaminetetraacetic acid
LFT	liver function test
LOAEL	lowest observed adverse effect level
LSLV	last subject last visit
MAD	multiple ascending dose
MCP	metacarpophalangeals
MRI	magnetic resonance imaging
N/A	not applicable
NOAEL	no observed adverse effect level
NRS	numeric rating scale
NSAID	nonsteroidal anti-inflammatory drugs
PAAP	patient assessment of arthritis pain

Abbreviation	Term
PCD	primary completion date
PD	pharmacodynamics(s)
PGx	pharmacogenomics(s)
PhGA	physician's global assessment
PI	principal investigator
PK	pharmacokinetic
PO	per os (oral)
PT	prothrombin time
PtGA	patient's global assessment
RA	rheumatoid arthritis
RNA	ribonucleic acid
SAE	serious adverse event
SAD	single ascending dose
SAP	statistical analysis plan
SC	subcutaneous
SDAI	simple disease activity index
SJC	swollen joint count
SLE	systemic lupus erthematosus
SOP	standard operating procedure
SRSD	single reference safety document
SUSAR	suspected unexpected serious adverse reaction
TBili	total bilirubin
TEAE	treatment emergent adverse event
TJC	tender joint count
TNF	tumor necrosis factor
TNF α	tumor necrosis factor alpha
TNFi	TNF inhibitors
UC	ulcerative colitis
UGT	uridine 5'-diphospho-glucuronosyltransferase
ULN	upper limit of normal
US	United States
VAS	visual analog scale
VZV	varicella zoster virus
WBC	white blood cells
WONCBP	women of non-childbearing potential

Appendix 2. 2010 ACR/EULAR Classification Criteria for Rheumatoid Arthritis^{24,25}

Presented below are the 2010 American College of Rheumatology (ACR)/European League Against Rheumatism (EULAR) classification criteria for rheumatoid arthritis.

Target population (Who should be tested?) must have:

- 1) have at least 1 joint with definite clinical synovitis (swelling)*
- 2) with the synovitis not better explained by another disease†

Classification criteria for RA (score-based algorithm: add score of categories A–D; a score of $\geq 6/10$ is needed for classification of a patient as having definite RA)‡

A. Joint involvement§		SCORE (A) _____
1 large joint¶	0	
2-10 large joints	1	
1-3 small joints (with or without involvement of large joints)#	2	
4-10 small joints (with or without involvement of large joints)	3	
>10 joints (at least 1 small joint)**	5	
B. Serology (at least 1 test result is needed for classification)††		SCORE (B) _____
Negative RF and negative ACPA	0	
Low-positive RF or low-positive ACPA	2	
High-positive RF or high-positive ACPA	3	
C. Acute-phase reactants (at least 1 test result is needed for classification)‡‡		SCORE (C) _____
Normal CRP and normal ESR	0	
Abnormal CRP or abnormal ESR	1	
D. Duration of symptoms§§		SCORE (D) _____
<6 weeks	0	
≥6 weeks	1	
		TOTAL SCORE (A+B+C+D) _____

A TOTAL Score of $\geq 6/10$ is needed for classification of a patient as having definite RA)‡

* The criteria are aimed at classification of newly presenting patients. In addition, patients with erosive disease typical of rheumatoid arthritis (RA) with a history compatible with prior fulfillment of the 2010 criteria should be classified as having RA. Patients with longstanding disease, including those whose disease is inactive (with or without treatment) who, based on retrospectively available data, have previously fulfilled the 2010 criteria should be classified as having RA.

† Differential diagnoses vary among patients with different presentations, but may include conditions such as systemic lupus erythematosus, psoriatic arthritis, and gout. If it is unclear about the relevant differential diagnoses to consider, an expert rheumatologist should be consulted.

‡ Although patients with a score of $<6/10$ are not classifiable as having RA, their status can be reassessed and the criteria might be fulfilled cumulatively over time.

§ Joint involvement refers to any *swollen* or *tender* joint on examination, which may be confirmed by imaging evidence of synovitis. Distal interphalangeal joints, first carpometacarpal joints, and first metatarsophalangeal joints are *excluded from assessment*. Categories of joint distribution are classified according to the location and number of involved joints, with placement into the highest category possible based on the pattern of joint involvement.

¶ “Large joints” refers to shoulders, elbows, hips, knees, and ankles.

“Small joints” refers to the metacarpophalangeal joints, proximal interphalangeal joints, second through fifth metatarsophalangeal joints, thumb interphalangeal joints, and wrists.

** In this category, at least 1 of the involved joints must be a small joint; the other joints can include any combination of large and additional small joints, as well as other joints not specifically listed elsewhere (eg, temporomandibular, acromioclavicular, sternoclavicular, etc.).

†† Negative refers to IU values that are less than or equal to the upper limit of normal (ULN) for the laboratory and assay; low-positive refers to IU values that are higher than the ULN but ≤ 3 times the ULN for the laboratory and assay; high-positive refers to IU values that are >3 times the ULN for the laboratory and assay. Where rheumatoid factor (RF) information is only available as positive or negative, a positive result should be scored as low-positive for RF. ACPA= anti-citrullinated protein antibody.

‡‡ Normal/abnormal is determined by local laboratory standards. CRP = C-reactive protein; ESR = erythrocyte sedimentation rate.

§§ Duration of symptoms refers to patient self-report of the duration of signs or symptoms of synovitis (eg, pain, swelling, tenderness) of joints that are clinically involved at the time of assessment, regardless of treatment status.

Appendix 3. Criteria for Classification of Functional Status in Rheumatoid Arthritis²⁶

Class I: Completely able to perform usual activities of daily living (self-care, vocational, and avocational).

Class II: Able to perform usual self-care and vocational activities, but limited in avocational activities.

Class III: Able to perform usual self-care activities, but limited in vocational and avocational activities.

Class IV: Limited in ability to perform usual self-care, vocational, and avocational activities.

Usual self-care activities including dressing, feeding, bathing, grooming, and toileting. Avocational (recreational and/or leisure) and vocational (work, school, homemaking) activities are patient-desired and age- and sex-specific.

Appendix 4. Prohibited Concomitant Medications

This is not an all-inclusive list. Study personnel should stay current and consult with their pharmacy to exclude all concomitant medications that are either moderate to potent CYP3A inhibitors or inducers.

Moderate to Potent CYP3A Inhibitors*	Moderate to Potent CYP3A Inducers**
Amprenavir	Avasimibe#
Amiodarone	Bosentan
Aprepitant	Barbiturates
Atazanavir	Carbamazepine#
Boceprevir	Efavirenz
Casopitant	Etravirine
Cimetidine	Mitotane#
Ciprofloxacin	Modafinil
Clarithromycin#	Nafcillin
Cobicistat#	Phenobarbital#
Conivaptan#	Phenytoin#
Darunavir	Rifabutin#
Diethyldithiocarbamate	Rifampin #
Diltiazem	St. John's Wort#
Dronedarone	Talviraline
Elvitegravir#	
Erythromycin	
Fluconazole	
Fluvoxamine	
Imatinib	
Indinavir#	
Itraconazole#	
Ketoconazole#	
Lopinavir#	
Mibefradil#	
Mifepristone (RU486)	
Nefazodone#	
Nelfinavir#	
Norfloxacin	
Posaconazole#	
Ritonavir #	
Saquinavir#	
Schisandra sphenanthera	
Telaprevir	
Telithromycin#	
Tipranavir#	
Tofisopam	
Troleandomycin#	
Verapamil	
Voriconazole#	

* All prohibited drugs that are CYP3A inhibitors require at least a 7 day or 5 half-lives (whichever is longer) washout prior to the first dose of study drug.
 Note: Amiodarone requires discontinuation at least 290 days (~5 half-lives, half-life averages ~58 days) prior to the first dose of study drug.

** All prohibited drugs that are CYP3A inducers require at least a 28 day or 5 half-lives (whichever is longer) washout prior to the first dose of study drug.

Notated as potent inhibitors or inducers.

It is recommended that subjects avoid consumption of grapefruit juice exceeding 8 ounces (~240 ml) total in a day while in the study.

In a situation where appropriate medical care of a subject requires the use of a prohibited CYP3A inhibitor or inducer:

Moderate to potent inhibitors and inducers of CYP3A are not permitted in the study EXCEPT in emergency situations requiring no more than one day of administration.

Note: Amiodarone and mitotane are not permitted for any duration due to their long half-lives. Topical (including skin or mucous membranes) application of antimicrobial and antifungal medications is permitted.

Appendix 5. Guidelines for Monitoring and Discontinuations

These guidelines for subject safety monitoring and discontinuation are to be applied to all subjects in this study. Additional individual subject monitoring is at the discretion of the investigator and dependent on any perceived safety concerns. Unscheduled clinical labs may be obtained at any time during the study to assess such concerns, and a subject may be withdrawn at any time at the discretion of the investigator.

Monitoring

The following laboratory abnormalities require re-testing within 1 week:

- Absolute neutrophil count $<2000/\text{mm}^3$; ($< 2 \times 10^9/\text{L}$)
- Hemoglobin $<9.0 \text{ g/dL}$;
- Platelet count below $<100,000/\text{mm}^3$; ($<100 \times 10^9/\text{L}$)
- Lymphocyte counts $<500 \text{ lymphocytes}/\text{mm}^3$; ($<0.5 \times 10^9/\text{L}$)
- Any single AST and/or ALT elevation ≥ 3 times the upper limit of normal (repeat laboratory testing should include albumin, creatine kinase, total bilirubin, direct and indirect bilirubin, GGT, PT [prothrombin time] with INR [international normalized ratio], and alkaline phosphatase), regardless of the total bilirubin. (Please note that 3 times the upper limit of normal increases in ALT, AST need confirmation on separate blood draw before undertaking thorough evaluation for liver injury);
- All potential treatment-related reports of rash will be followed up until resolution or in agreement with Pfizer.
- Positive urine β -hCG test, the subject will have study drug interrupted and a serum sample collected on the same day (or as soon as possible) and submitted to the central laboratory for β -hCG testing.

Discontinuation

The sponsor's Clinical team should be notified as soon as possible and subject treatment will be discontinued and the subject withdrawn from this study for:

- Two sequential hemoglobin value $<8.0 \text{ g/dL}$ or one that drops 2 g/dL below baseline
- Two sequential absolute neutrophil counts $<750/\text{mm}^3$; ($<0.75 \times 10^9/\text{L}$)
- Two sequential platelet counts $<75,000/\text{mm}^3$;($<75 \times 10^9/\text{L}$)
- Two sequential lymphocyte counts $<500 \text{ lymphocytes}/\text{mm}^3$; ($<0.5 \times 10^9/\text{L}$)

- Two sequential AST or ALT elevation ≥ 3 times the upper limit of normal with at least one total bilirubin value ≥ 2 times the upper limit of normal^a
- Two sequential AST or ALT elevation ≥ 3 times the upper limit of normal accompanied by signs or symptoms consistent with hepatic injury^a
- Two sequential AST or ALT elevation ≥ 5 times the upper limit of normal, regardless of total bilirubin or accompanying signs or symptoms^a
- Serious infections, defined as any infection (viral, bacterial, and fungal) requiring parenteral antimicrobial therapy, hospitalization for treatment, or meeting other criteria that require the infection to be classified as serious adverse event
- Other serious or severe AEs, at the discretion of the investigator or sponsor
- Female subjects found to be pregnant during the study; For women of child-bearing potential with any positive urine β -hCG test, the subject will have study drug interrupted and a serum sample submitted to the central laboratory for β -hCG testing
- Subjects who are treated with any prohibited medication during the course of the study
- Serious or severe drug-related rash at the discretion of the investigator or sponsor. (See [Section 7.2.11](#))
- Subjects who require rescue doses of acetaminophen/paracetamol or opioid for more than 10 consecutive days or within the last 7 days before the last dose should be discontinued from the trial;
 - a In each case, there is a need for additional investigations, such as review of ethanol, recreational drug and dietary supplement consumption; testing for acute hepatitis A, B or C infection and biliary tract imaging should be promptly discussed with the Pfizer medical monitor or designee.

If a patient has any clinically significant, treatment emergent abnormalities at the conclusion of the study, the medical monitor (or designated representative) should be notified and every effort should be made to arrange follow-up evaluations at appropriate intervals to document the course of the abnormality. All abnormal laboratory events of clinical significance should be followed until the laboratory values have returned to the normal or baseline levels or is otherwise considered stable by the investigator.

Appendix 6. Disease Activity Score (DAS) Assessments¹

DAS-28-4 (CRP) Assessment

The formula for calculation of DAS28-4 (CRP) using 4 components:

- Swollen Joints (0–28);
- Tender Joints (0–28);
- CRP
- Patient's Global Assessment of Arthritis (PtGA) (0 – 100 mm VAS).

$DAS28-4 (CRP) = 0.56 \sqrt{DAS\ 28\ tender\ joint\ count} + 0.28 \sqrt{DAS\ 28\ swollen\ joint\ count} + 0.36 \ln(CRP\ [mg/L] + 1) + 0.014 (PtGA\ [mm]) + 0.96$

DAS-28-4 (ESR) Assessment

The formula for calculation of DAS28-4 (ESR) using 4 components:

- Swollen Joints (0–28);
- Tender Joints (0–28);
- Erythrocyte Sedimentation Rate (ESR);
- Patient's Global Assessment of Arthritis (PtGA) (0 – 100 mm VAS).

$DAS28-4 (ESR) = 0.56 \sqrt{DAS\ 28\ tender\ joint\ count} + 0.28 \sqrt{DAS\ 28\ swollen\ joint\ count} + 0.70 \ln (ESR\ [mg/L] + 0.014 (PtGA\ [mm]))$

Appendix 7. Patient's Assessment of Arthritis Pain (PAAP)

MY PAIN AT THIS TIME IS:
(PLEASE MAKE AN X MARK ON THE LINE BELOW.)

No _____ Most Severe
Pain _____ Pain

[Note: Scale will be 100 mm in length]

Appendix 8. Patient's Global Assessment (PtGA) of Arthritis

CONSIDERING ALL THE WAYS YOUR ARTHRITIS AFFECTS YOU, HOW ARE YOU FEELING TODAY?

(PLEASE MAKE AN X MARK ON THE LINE BELOW.)

Very Well _____ Very Poorly

[Note: Scale will be 100 mm in length]

Appendix 9. Physician's Global Assessment (PhGA) of Arthritis

THE PATIENT'S ARTHRITIS AT THIS TIME IS:
(PLEASE MAKE AN X MARK ON THE LINE BELOW.)

Very _____ Very
Good _____ Poor

[Note: Scale will be 100 mm in length]

Appendix 10. Oral Corticosteroid Equivalents^{28,29,30,31,32}

The following is a summary of corticosteroid equivalents.

Oral corticosteroids – subjects already taking oral corticosteroids must be on a stable dose of ≤10 mg/day of prednisone or equivalent for at least 4 weeks prior to first dose of study drug.

Compound	Equivalent Dose (mg)
Prednisone	10
Prednisolone	10
6 α -methylprednisolone	8
Triamcinolone	8
Betamethasone	1.2
Dexamethasone	1.5
Hydrocortisone	40
Cortisone	50
Deflazacort	12
Cloprednol	5
Prednylidene	12

Note: these dose relationships apply to oral administration.

Appendix 11. Allowed Opioids and Approximate Equivalent Morphine Doses Of Opioid Analgesics^{33,34}

Common opioid analgesics

Drug	Maximum Allowed Total Daily Dose	Relative potency to oral morphine	Half-Life
Morphine	30 mg	1	1.5 – 4 hrs
Hydrocodone (Vicodin, Lortab)	30 mg	1	3.8 – 4.5 hrs
Hydromorphone (Dilaudid)	7.5 mg	4	2.5 hrs
Meperidine (Demerol, Pethidine)	300 mg	0.1	3.2 – 3.7 hrs
Methadone (Dolophine, Methadose, Physeptone)	10 mg	3.0	23 hrs
Codeine (Paveral, Tylenol #2 and #3)	200 mg	0.15	2.5 – 3.5 hrs
Oxycodone [Roxicodone; Percocet, Tylox]	15 mg	~2	3.2 hrs
Tramadol [Ultram, Zydol; Zamadol, Ultracet, Tramal]	300 mg	~0.1	4.7 – 5.1 hrs
Propoxyphene HCl (Darvon, Darvocet, Doloxene) Propoxyphene napsylate (Darvon-N, Darvocet-N 100)	300 mg propoxyphene HCl 400 mg propoxyphene napsylate	~0.1	6-12 hrs; 30-36 hrs. for active metabolite (norpropoxyphene)

Sites should contact project team for acceptable alternative preparations and related data.

Appendix 12. Common Terminology Criteria for Adverse Events v4.03 (CTCAE)-Dermatology

The NCI Common Terminology Criteria for Adverse Events v4.03 is a descriptive terminology that can be utilized for Adverse Event (AE) reporting. A grading (severity) scale is provided for each AE term. One page of the Dermatology/Skin Category is presented, which contains listings for Pruritus, Rash/Desquamation, and Rash: Acne/acneiform.

Skin and subcutaneous tissue disorders					
Adverse Event	Grade				
	1	2	3	4	5
Pruritus	Mild or localized; topical intervention indicated	Intense or widespread; intermittent; skin changes from scratching (eg, edema, papulation, excoriations, lichenification, oozing/crusts); oral intervention indicated; limiting instrumental ADL	Intense or widespread; constant; limiting self care ADL or sleep; oral corticosteroid or immunosuppressive therapy indicated	-	-
Definition: A disorder characterized by an intense itching sensation.					
Purpura	Combined area of lesions covering <10% BSA	Combined area of lesions covering 10 - 30% BSA; bleeding with trauma	Combined area of lesions covering >30% BSA; spontaneous bleeding	-	-
Definition: A disorder characterized by hemorrhagic areas of the skin and mucous membrane. Newer lesions appear reddish in color. Older lesions are usually a darker purple color and eventually become a brownish-yellow color.					
Rash acneiform	Papules and/or pustules covering <10% BSA, which may or may not be associated with symptoms of pruritus or tenderness	Papules and/or pustules covering 10 - 30% BSA, which may or may not be associated with symptoms of pruritus or tenderness; associated with psychosocial impact; limiting instrumental ADL	Papules and/or pustules covering >30% BSA, which may or may not be associated with symptoms of pruritus or tenderness; limiting self care ADL; associated with local superinfection with oral antibiotics indicated	Papules and/or pustules covering any % BSA, which may or may not be associated with symptoms of pruritus or tenderness and are associated with extensive superinfection with IV antibiotics indicated; life-threatening consequences	Death
Definition: A disorder characterized by an eruption of papules and pustules, typically appearing in face, scalp, upper chest and back.					
Rash maculo-papular	Macules/papules covering <10% BSA with or without symptoms (eg, pruritus, burning, tightness)	Macules/papules covering 10 - 30% BSA with or without symptoms (eg, pruritus, burning, tightness); limiting instrumental ADL	Macules/papules covering >30% BSA with or without associated symptoms; limiting self care ADL	-	-
Definition: A disorder characterized by the presence of macules (flat) and papules (elevated). Also known as morbilliform rash, it is one of the most common cutaneous adverse events, frequently affecting the upper trunk, spreading centripetally and associated with pruritus.					

Rash/desquamation and erythema multiforme progressing to Grade 2, acne/acneiform rash or pruritus progressing to Grade 3 are the severity levels for permanently discontinuing a subject from investigational product.

Pruritus progressing to Grade 2 sustained (>4 days) is cause to permanently discontinue investigational product.

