7.2.11. Dermatological Assessments

All subjects will have a dermatological full body exam at Screening Visit. Skin lesions will be evaluated as defined in the National Cancer Institute Common Toxicity Criteria for Adverse Events v4.03 (See [Appendix 12](#), for Dermatology/Skin Category) and managed as shown below.

Table 7. Management of Dermatological Events

Dermatologic Event (CTCAE v 4.03)*	Course of Management
Acne/Acneiform Rash/Maculopapular Rash	
Grade 1/2	
 Investigator’s discretion for withdrawing investigational product. Execute reasonable monitoring. Consider treatment with topical agents such as clindamycin or corticosteroids.
Grade 3	
 Discontinue investigational product. Monitor to resolution (defined as a Return to Baseline status). Consider treatment with topical agents such as clindamycin or corticosteroids.
Pruritus	
Grade 1 Mild or localized	
 Investigator’s discretion for withdrawing investigational product. Execute reasonable monitoring. Consider treatment with topical agents such as clindamycin or corticosteroids.
Grade 2 Intense or widespread	
 Discontinuation of the investigational product may not be required unless condition is sustained >4 days or at the investigator’s discretion. Execute reasonable monitoring. Consider treatment with topical agents such as clindamycin or corticosteroids.
Grade 3 Intense or widespread and interfering with activities of daily living	
 Permanently discontinue investigational product. Monitor to resolution (Return to Baseline). Consider treatment with topical agents such as clindamycin or corticosteroids.

* Refer to [Appendix 12](#) for clarification.

Herpetiform Rash

For any occurrence of a suspected herpetiform rash (eg, herpes zoster and herpes simplex), specimens for viral DNA analysis will be obtained: A swab of the affected area will be collected for confirmation; a blood sample for viral surveillance will be collected for the analysis of viral load. Details for these collections will be provided in the laboratory manual.

Drug-Related Rash

All potential drug related reports of rash will be followed up until resolution or clinically stable or in agreement with Pfizer.

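### Appendix 12 makes Grade 2 rash/desquamation a permanent stop, while Table 7 leaves Grade 2 maculopapular rash, most plausibly the same event, to the investigator; no precedence is stated

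*Protocol*

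**What the plan says.** Section 7.2.11 of the protocol sets the grading standard: "Skin lesions will be evaluated as defined in the National Cancer Institute Common Toxicity Criteria for Adverse Events v4.03". The same sentence points to Appendix 12 for the skin category and to Table 7 for management.

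Table 7 puts three events under one heading, "Acne/Acneiform Rash/Maculopapular Rash". At Grade 1/2 it gives the investigator "discretion for withdrawing investigational product". At Grade 3 it says to discontinue, without saying permanently. For pruritus it is more exact. At Grade 2, "Discontinuation of the investigational product may not be required unless condition is sustained >4 days" (or the investigator so decides). At Grade 3, "Permanently discontinue investigational product". The table's header carries a footnote sending the reader to Appendix 12 for clarification.

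Appendix 12 says that it prints one page of the CTCAE v4.03 skin category. The rows shown are pruritus, purpura, acneiform rash and maculo-papular rash. Two stop rules follow: "Rash/desquamation and erythema multiforme progressing to Grade 2, acne/acneiform rash or pruritus progressing to Grade 3 are the severity levels for permanently discontinuing" the subject from treatment, and "Pruritus progressing to Grade 2 sustained (>4 days) is cause to permanently discontinue investigational product".

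Appendix 5, the discontinuation list, leaves serious or severe drug-related rash to investigator or sponsor judgement and refers back to Section 7.2.11.

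**The concern.** These are participant-safety stopping rules, and two of them appear to give different actions for the same event. If rash/desquamation in Appendix 12 is maculopapular rash, Grade 2 is a matter of judgement in the body of the protocol and a mandatory permanent stop in the appendix. Two sites could treat the same Grade 2 rash differently, each citing the protocol. A monitor could also record a deviation at a site that did what Table 7 allows.

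The event has been seen on this drug. Table 1 (Section 1.5.1) reports maculopapular rash in first-in-human subjects on active drug and in none on placebo. What is at stake is consistent stopping at Grade 2, not whether rash is detected. Rash is assessed throughout the schedule of activities, unexplained rash is referred for dermatological evaluation, and Grade 3 rash stops treatment.

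**Working it through.** No statistical input is involved, so the check is a comparison of texts.

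**Step 1. What rash/desquamation refers to.** The introduction to Appendix 12 names three listings: pruritus, rash/desquamation and acne/acneiform rash. The pruritus and acneiform rows match two of these. The only other rash row is maculo-papular, so that is the most plausible match. It remains an inference: the introduction is inexact (four rows are printed and purpura is not named), and the stop rule also names erythema multiforme, which has no printed row.

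**Step 2. Each Appendix 12 trigger against Table 7.**

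| Event and grade | Table 7 | Appendix 12 | Result |
|---|---|---|---|
| Rash/desquamation, Grade 2 (read as maculopapular) | Investigator decides | Permanent stop | Conflict, given step 1 |
| Erythema multiforme, Grade 2 | Not listed | Permanent stop, no printed grading | Gap |
| Acneiform rash, Grade 3 | Discontinue | Permanent stop | Same grade, action worded differently |
| Pruritus, Grade 2, more than 4 days | Stop may be required, permanence not stated | Permanent stop | Same threshold, action worded differently |
| Pruritus, Grade 3 | Permanent stop | Permanent stop | Agree |

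Count: 1 conflict + 1 gap + 3 at the same grade = 5 triggers. Because three of the five repeat Table 7's thresholds, a site would reasonably read the Appendix 12 rules as operative and not as background to the grading page.

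**Step 3. Precedence.** Section 7.2.11 sends management to Table 7, and Appendix 5 points to Section 7.2.11. Both favour Table 7. Table 7's footnote points the other way, to the appendix that holds the stricter rule. None of these says which text prevails or cancels the other.

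**Step 4. What the documents say about frequency.** The maculopapular row of Table 1, active subjects, over its seven cohorts in order: 0 + 1 + 1 + 0 + 0 + 0 + 2 = 4. One case followed a single 100 mg dose, one occurred at 100 mg BID and two at 200 mg BID; 3 were moderate and 1 severe. Placebo: 0. There were none at 200 mg QD, this trial's dose, and none at 400 mg QD. The 200 mg QD cohort is listed with N=8 over both arms, and multiple dosing lasted 14 days against 8 weeks here. The 100 mg BID case was at the same total daily dose (2 × 100 = 200 mg). Table 1 uses mild, moderate and severe rather than CTCAE grades, so a Grade 2 rate at 200 mg QD cannot be derived.

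**The case against.** The strongest defence is that the texts can be read together: Table 7 gives general discretion, and its footnote sends the reader to Appendix 12 to learn when stopping is required. A site that stops at Grade 2 then complies with both. This is a fair reading and it rules out saying that Table 7 plainly prevails. It does not remove the conflict. A footnote offering clarification is not a precedence clause, and a site that relies on Table 7's discretion still breaches the appendix.

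The practical risk is also limited. The worst case is continued dosing at Grade 2 under a physician's judgement. Unexplained rash is biopsied unless an exemption applies, potentially drug-related rash is followed up, and the investigator may withdraw a subject at any time. That stands, and it limits the weight of the point.

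Three stronger readings are tempting but not supported:

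- A reader might infer that the Appendix 12 stop is unworkable whatever rash/desquamation means, because no printed row grades it. But Section 7.2.11 adopts CTCAE v4.03 as a whole and the appendix reproduces one page. Absence from that page does not show absence from the standard.
- A reader might count two of the five triggers as contradicting Table 7. Erythema multiforme is omitted from Table 7, not treated differently there.
- A reader might conclude that the permanent stop is the correct Grade 2 action. The documents do not say so; the threshold is a clinical choice.

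**Conclusion.** The point holds as one conflict between two operative stopping rules, at Grade 2 maculopapular rash, with no stated precedence. It rests on reading rash/desquamation as maculo-papular rash, which is well supported but inferred. That the term has no printed row is certain.

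Two lesser defects sit beside it and do not depend on that inference. The erythema multiforme stop has no entry in Table 7 and no printed grading. For acneiform rash at Grade 3, Table 7 orders discontinuation where Appendix 12 orders permanent discontinuation, although Table 7 itself uses the permanent wording for Grade 3 pruritus.

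The number of subjects affected is unknown, and no effect on the primary analysis is shown. The point should be fixed because it is a safety rule, the correction is cheap, and the rash has occurred on active drug.

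**What to change.** Put one rule in one place:

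- In Appendix 12, replace rash/desquamation with rash maculo-papular.
- Give maculopapular rash its own row in Table 7 with a single Grade 2 action, repeated identically in Appendix 12. Use the stricter permanent stop unless the sponsor's clinical team deliberately chooses discretion and deletes the Appendix 12 clause.
- Add erythema multiforme to Table 7, with the grading criteria the sponsor intends.
- Use either discontinue or permanently discontinue consistently for each event and grade.
- State that Table 7 governs and that Appendices 5 and 12 defer to it.

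The cost is a wording amendment and a notice to sites, with no new procedures. If the stricter rule is kept, there may be a few extra treatment stops among about 60 subjects. The documents give no basis for a firmer number.
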